# Emergency Medicine Prospective Protocol

## Background and Study Rationale

This document serves as the study's research protocol and the described study will be conducted in compliance with the provisions set forth in the protocol as well as, Good Clinical Practice standards, associated federal regulations, and all applicable Lurie research requirements.

This study will be conducted in full accordance with all applicable Lurie Children's Hospital IRB Policies and Procedures and all applicable Federal and state laws and regulations.

### 1 Introduction

Motor vehicle collisions (MVCs) remain the leading cause of unintentional injury deaths among children in the United States (U.S.) and racial/ethnic minority children are disproportionately impacted as suboptimal child passenger safety behaviors are more prevalent in some communities. Existing universal approaches to promote child passenger safety have fallen short of ensuring that all child passengers are correctly using size-appropriate child passenger restraints according to guidelines published by the American Academy of Pediatrics and the National Highway Traffic Safety Administration. Precision prevention programs are urgently needed to improve child passenger safety behaviors among caregivers who have not been responsive to guidelines, laws, and public education campaigns. The proposed research will test the efficacy of Tiny Cargo, Big Deal (TCBD), an emergency department (ED)-based precision prevention intervention grounded in Self-Determination Theory. TCBD integrates personalized counseling based on principles of motivational interviewing (MI) and eHealth components including a tailored educational mobile friendly website "site" and short message service (SMS) communications with the goal of improving child passenger safety. We hypothesize that by providing tailored child passenger safety education and personalized skills for restraint use in a manner that supports autonomous motivation the TCBD intervention will be more efficacious than universal approaches (laws/guidelines) for realizing correct use of size-appropriate child passenger restraints.

#### 1.1 Background and Relevant Literature

The overarching scientific premise of the proposed study is derived from the published literature demonstrating that the emergency department (ED) can be a site of screening to identify suboptimal child passenger safety behaviors and can serve as a site of intervention, that tailored child passenger safety information can increase parental knowledge, and that eHealth holds promise for child passenger safety education. Additionally, our own pilot work in the ED suggests that child passenger safety behaviors can be improved and disparities reduced through a brief counseling session and tailored educational brochures. Despite this collective evidence, suboptimal child passenger safety behaviors are prevalent and a key contributor to injuries sustained in motor vehicle collisions (MVCs).

Motor vehicle collisions (MVCs) remain a significant and costly public health problem in the United States (U.S.). MVCs are *the #1 cause* of unintentional injury-related deaths among 4-12 year olds and a leading cause of unintentional injury-related deaths among younger children. **In fact, more U.S. children die from MVCs than die of heart disease, chronic lower respiratory diseases, influenza/pneumonia, or sepsis each year.** Child passenger fatality rates have been stagnant around 650 per year from 2010 and 2014. In 2015, crash fatality rates in the U.S. rose by the largest percent in 50 years. Non-fatal injuries also represent an enormous burden. In 2013, more than 131,000 children received emergency treatment for non-fatal injuries sustained in MVCs, and more than half of these children required hospital admission or transfer

# Emergency Medicine Prospective Protocol

to another ED. Childhood survivors of MCVs can experience lifelong sequelae, including mobility impairments, irreversible brain or spinal cord injuries, and post-traumatic stress disorder.

Universal strategies to promote child passenger safety provide recommendations for the population as a whole and are disseminated in national guidelines, state laws, and public education campaigns. These strategies have reached many caregivers but **current recommendations are not adopted for all child passengers.** Precision prevention strategies, targeted to those who have not responded to universal strategies, are urgently needed to reduce unintentional injuries from MVCs. Suboptimal child restraint system (CRS) use is lowest for infants, with about 10% prematurely using a forward-facing car seat with a harness or booster seat. Suboptimal CRS use increases considerably after a child's first birthday; roughly 30% of toddlers use a booster seat or seat belt alone and >50% of elementary school age children use a seat belt alone when they would benefit from a more protective restraint. The greatest risk for injury is among children who travel unrestrained. This is permitted by caregivers in increasing proportions as children progress from toddlers (5%) to teens (15%). Proportions of fatally injured unrestrained children increase from 27% among <4 year olds to 45% for 8-12 year olds.

Prior child passenger safety research has generally encouraged use of car seats or booster seats for children in traditional age categories. We propose to move beyond one-size-fits-all age-based approaches with an innovative precision prevention intervention that: 1) *targets caregivers with suboptimal child passenger safety behaviors*; 2) *integrates child size, anticipated growth trajectory, and current CRS into personalized recommendations for correct use of a size-appropriate restraint*; 3) *tailors messages on caregiver race/ethnicity and Self-Determination Theory constructs (autonomy, relatedness, competence)*; and 4) has a second level of *increased intensity* to address caregivers who do not change their child passenger safety behavior by Month 6 of the study.

This proposal aligns with the NICHD Pediatric Trauma Research Program goal to reduce morbidity and mortality in childhood through injury prevention. The national strategy on highway safety has become focused on the goal of moving "Toward Zero Deaths" on U.S. roadways. In addition, the CDC has declared **child passenger safety is a "Winnable Battle"** based on the large potential impact and known effective strategies to address transportation-related injuries. Healthy People 2020 Objectives for Unintentional Injury Prevention include increasing age-appropriate child restraint system (CRS) use in children with age-group specific targets that are far from optimal due to limited adoption of current recommendations.

The fact that seat belt use reduces the risk of injury is indisputable. However, **vehicle seats and seat belts are designed for adults not children.** Children experience dramatic physical and biomechanical changes before reaching the stature (around a height of 57") and maturity necessary to achieve proper fit with an adult seat belt in a vehicle seat. To accommodate the range of child growth and development, distinct CRS modes (rear-facing car seats, forward-facing car seats, and booster seats), have been designed to provide greater levels of protection than an adult seat belt alone can provide to a child in a crash. CRS, used correctly, prevent injury and save lives. Rear-facing CRS use until age 2 lowers the odds of serious injury in a frontal crash 5-fold compared with forward facing. Forward-facing car seats reduce risk of serious injury for toddlers by 70% and risk of death by 25% compared with seat belts. Booster seats cut the risk of non-fatal injury among 4 to 7-year-old children in half compared with seat belts alone. This evidence provides the foundation for the 2011 updates to child passenger safety recommendations from the American Academy of Pediatrics (AAP), which state a child should: 1) remain rear-facing as long as possible, until at least age 2 or reaching the weight or

# Emergency Medicine Prospective Protocol

height limits of their rear-facing CRS; 2) then use a forward-facing harness restraint until reaching the weight or height limits of that CRS; 3) then use a booster until proper seat belt fit can be achieved usually between ages 8 and 12; and 4) always ride in a back seat.

**Addressing suboptimal child passenger safety in minority populations is crucial to eliminate disparities.** Death rates among passengers <13 years are significantly higher for black compared with white children (0.73 vs. 0.57 per 100,000) and fatally injured black children are almost twice as likely to have been unrestrained compared with white children (45% vs. 26%). In national observational data, we found suboptimal child passenger safety behaviors, including premature transitions to a less protective restraint and travelling unrestrained, were more common among minority children. In survey data we obtained from caregivers in two Michigan EDs, racial differences in child passenger safety behaviors persisted after adjusting for caregiver education, income, and sources of child passenger safety information.

**Research shows that ED visits are a window of opportunity for behavior change.** We have selected the ED as the location to initiate our intervention because ED visits are frequent among U.S. children, totaling more than 25 million annually. In 2014, about 20% of children visited a hospital ED at least once. Children who utilize the ED may have limited access to primary care services and many come from poor and minority populations. As a result, some families in the ED have less exposure to primary care-based injury prevention programs. Public health challenges, including child passenger safety, adult seat belt use, smoking cessation, substance abuse, and violence prevention have been addressed in the ED. Conducting our study in a community hospital ED will complement the literature from child passenger safety studies conducted in large children's hospital EDs and be more generalizable to the types of EDs that provide emergency care to most U.S. children.

## 2 Study Objectives

The proposed randomized, adaptive trial will test the efficacy of a selective intervention, *Tiny Cargo, Big Deal* (TCBD), to improve child passenger safety among caregivers who are not adherent to current national recommendations. The TCBD intervention, grounded in Self-Determination Theory (SDT) and developed as a part of [name] K23 award, consisted of a brief motivational interviewing (MI) session in the ED and a mailed brochure tailored on child age, size, and restraint use. TCBD proved feasible and acceptable with *significant promise for improving child passenger safety behaviors* at 6-month follow-up. We have enriched TCBD based on pilot participant feedback to include a streamlined ED counseling session, new eHealth components, and one booster MI session delivered by phone. To replace the paper brochures, we have designed a prototype mobile friendly web "site" that has shown positive results in usability testing. The study site will be optimized for mobile devices and provide to the intervention group with continuous access to *personalized, precise* child passenger safety information. We will augment the intervention with tailored short message service (SMS) communications (i.e., text messages) that facilitate bi-directional flow of information after the ED visit.

We hypothesize that a precision prevention intervention (TCBD) that provides tailored child passenger safety education and personalized skills for restraint use in a manner that supports autonomous motivation will be more efficacious than universal approaches (laws/national guidelines) for realizing correct use of a size-appropriate child passenger restraint. The primary outcomes, size-appropriate restraint use and the Child Passenger Safety Score (CPaSS), will be assessed with direct observation at scheduled, in-person appointments and remote observation of digital photographs submitted by caregivers in response to unscheduled text messages.

# Emergency Medicine Prospective Protocol

We will test our hypothesis using a randomized adaptive trial design with the following aims: **Aim 1:** To test the efficacy of the TCBD intervention compared to usual care for improving primary outcomes [i.e., size-appropriate restraint (dichotomous) and CPaSS-D (numeric)] at 6 and 12 months. **Aim 2:** To use latent growth curve models to identify characteristic trajectories for the CPaSS-R observed in digital photographs over the 12 study months and assess for correlates of the trajectory types. This innovative, theoretically grounded research will have long-standing impact on child passenger safety by informing the best methods to increase correct use of size-appropriate child restraint systems among caregivers of diverse backgrounds at the point they interact with the health care system. The work has the potential for wide-scale implementation in the ED and for translation to primary care offices, schools, and community settings with an ultimate goal of eliminating child passenger safety disparities and reducing the number of childhood injuries from MVCs.

## **2.1 Primary Objectives**

The primary objectives of this efficacy trial are to:

- 1) test the efficacy of the TCBD intervention compared to usual care for improving primary outcomes [i.e., size-appropriate restraint (dichotomous) and the Child Passenger Safety Score (CPaSS) (numeric)] assessed at 12 months
- 2) use latent growth curve models to identify characteristic trajectories for the CPaSS observed in digital photographs submitted to the study team by caregivers over the 12 study months.

Correlates of the trajectory types will be assessed

## **2.2 Secondary Objectives**

Additionally, we will determine moderators (caregiver sex, race, child age) and mediators (Self-Determination Theory constructs of autonomy, relatedness, competence; emotional state at ED recruitment) of the intervention effects at 12-month follow-up.

Finally, we plan a cost analysis of the intervention to inform wider dissemination and implementation in settings outside of the ED. We will measure the total costs of the intervention from participant and health system perspectives by gathering estimates of intervention resource requirements, including personnel costs, implementation time, participant time, and material costs. We will calculate costs of the intervention per child. Net costs (savings) will be calculated by subtracting mean costs per participant in the control condition from mean costs per participant who receive the basic TCBD and the enhanced TCBD interventions. We will also estimate cost-effectiveness as measured by dollars per caregiver using a size-appropriate CRS and using the CRS correctly

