## ***3.2 Allocation to Interventional Group***

After completing the baseline survey, all caregivers will be randomized into one of two groups: 1) TCBD intervention group, or 2) control group. Computerized, block randomization (block sizes from four to eight) will be applied to assign eligible caregivers to the TCBD intervention or control group in a 3:1 ratio. Blocks will be stratified by age groups related to child passenger safety recommendations (<2 years – rear-facing CRS, 2-4 years – forward-facing CRS, 5-10 years – booster seat) and the child passenger safety behavior that led to eligibility for study (not using the recommended restraint currently or planning a premature transition in the coming 6 months).

After the 6-month follow-up assessment, caregivers in the intervention group only who continue suboptimal CRS use will be re-randomized by computer in a 1:1 ratio to receive either the basic or enhanced intervention. The enhanced TCBD will include one additional motivational interviewing (MI) session by phone in Month 7/8 and one to two additional tailored text messages in Months 7-12 (total of 7 tailored tips during these months compared to 4 tailored tips for those in the basic TCBD). The extra text messages will be sent to those in the enhanced TCBD group until size-appropriate restraint use is observed. Caregivers receiving enhanced TCBD will be encouraged to obtain a free seat check with a certified child passenger safety technician (CPST) in the community. The primary outcomes (size-appropriate CRS use and CPaSS) will be assessed in-person at Months 6 and 12. The secondary outcome, the CPaSS trajectory, is a measure of correct and consistent restraint use in response to the intervention and will be assessed by scoring photographs submitted by caregivers (Months 1-5; 7-11).

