# Emergency Medicine Prospective Protocol

Measured weight and length/height	ED, 6, and 12
Self-Determination Theory Constructs	
Treatment Self-Regulation Questionnaire 	ED/Baseline, 6, and 12
Confident rulers and Perceived Competence Scale 	ED/Baseline, 6, and 12
Health Care Climate Questionnaire 	12 months
Health Literacy and Numeracy	
The Newest Vital Sign 	6 months
Caregiver Emotional State, Stress, Coping	
State-Trait Anxiety Inventory 	ED/Baseline
Risk Behavior Diagnosis Scale 	ED/Baseline
Parenting stress index	ED/Baseline
Marlowe-Crowne Social Desirability Scale 	6 months
Child Passenger Safety Hassles Scale 	ED/Baseline, 6, and 12

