## 6 Statistical Plan

### 6.1 Sample Size and Power Determination

Briefly, our calculations are based on two-sample comparisons between groups (e.g., control and TCBD) using results from our pilot study that assessed percent size-appropriate child passenger safety behaviors at 6-month follow-up (referred to as the “response rate” below). For analyses involving multiple time points, these calculations represent a conservative lower bound on the power that would only be achieved if the effective sample equals 1 observation per person (i.e. perfect within-individual correlation). For the calculations below we assume: a) 17% response rate among controls; b) 25% response rate among TCBD caregivers at 6 Month (with 75% of TCBD caregivers re-randomized); and c) only 80% of the target sample (n=204 controls and n=516 TCBD in the initial dichotomy) will be available for analysis at follow-up. Components (a) and (b) are based on pilot data where the control group received generic educational materials and outcomes were assessed at 6-months. Component (c) is a conservative correction for attrition. For Aim 2, we estimated power while accounting for uncertainty in the group sizes by simulating response and re-randomization patterns according to the above probabilities and testing for significant between-group differences; this process was repeated 10,000 times and the power was estimated as the percent of replications in which a between-group difference was identified. Binary Outcome: For the binary response case, if the observed response rate is at least 29.4% among those receiving enhanced TCBD, it can be reliably (>80% power) distinguished from a control response rate of 17%. Analogously, a response rate of at least 27.6% among basic intervention would be reliably (>80% power) distinguished from control. Converted to Cohen's  $h$ , both differences reflect small-to-medium effect sizes ( $h = 0.30$  and  $h = 0.26$ , respectively). Numeric Outcome (CPaSS): If the standardized mean difference (i.e. Cohen's  $D$ ) is  $>0.25$  (a small-to-medium effect size), we can reliably distinguish between control and basic TCBD conditions. Similarly, if  $D \geq 0.28$ , a small-to-medium effect size, we will have sufficient power (80%) to distinguish the control and enhanced TCBD conditions. Aim 2: Monte Carlo studies of linear latent trajectory models indicate that a medium level of heterogeneity among the slopes and/or intercepts of the trajectories can be reliably recovered (power  $> 80\%$ ) with a total sample size of  $n=200$ , with power exceeding 95% when the level of heterogeneity is high; given that our sample size soundly exceeds 200, we expect sufficient ability to determine the underlying characteristic trajectory types. Nevertheless, we further justify our sample size with a brief simulation study. Assuming a final sample size of 720, conservatively assuming individuals are only measured at an average of 25% of the 12 monthly assessments, we simulate data from a population with four equally likely trajectory types: consistently low, consistently high, linearly decreasing, and starting high then dropping off. Because we have no basis for estimating variability in the score, we assumed mean/variance equivalence, consistent with the Poisson distribution. Due to the time required to fit such models, we only completed 200 simulation replications, where we were able to correctly conclude (based on BIC) that there were four

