## 6.2 Statistical Methods

All subjects, once randomized, will be included in an intention-to-treat analysis and outcomes will be collected even if the caregiver does not engage in the randomly assigned intervention. We will evaluate randomization by testing for covariate (e.g. demographic characteristics) balance between initial treatment groups, and between the re-randomized treatment groups created after the 6-month follow-up. If significant differences are observed, we will adjust for these variables or conduct stratified analyses. All statistical hypothesis tests and power calculations will use a two-sided = 0.05.

**Aim 1:** To test the efficacy of the TCBD intervention compared to usual care for improving primary outcomes [i.e., size-appropriate restraint (dichotomous) and CPaSS (numeric)] at 12 months. We hypothesize greater proportions of children will be using a size-appropriate restraint and higher CPaSS among caregivers in the intervention groups (basic and enhanced) compared with the control group (usual care) at the 12-month assessment. **Statistical Analysis:** Our primary analytic tool for estimating treatment effects will be generalized linear models (GLMs), and for analyses involving joint analysis of multiple follow-up data points, we will use generalized linear mixed models (GLMMs), which allows direct modeling of the correlations between data points (e.g. repeated measurements on individuals), and the inclusion of individuals with incomplete data (e.g. missing time points). The GLM(M) framework also allows simple controlling for confounders (if necessary) through their inclusion in the model as covariates. For the analysis of binary outcomes, we will use logistic GLM(M)s and for numeric outcomes (CPaSS-D) we will initially specify linear (Gaussian) GLM(M)s; this choice will be scrutinized by analyzing model diagnostics. The primary inferential target will be the coefficient for the treatment group indicator, making this effectively equivalent to ANCOVA. Adjustment for the baseline measurement is important for guarding

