**SubAim:** We will determine moderators (caregiver sex, race, child age) of the intervention effects and mediators (Self-Determination Theory constructs of autonomy, relatedness, competence; emotional state at ED recruitment). We hypothesize that disparities in CRS use can be reduced through a tailored intervention that increases autonomous motivation, competence, and relatedness for correct CRS use. **Statistical Analysis:** **Moderation:** Within the GLM(M) modeling framework described above, we will evaluate moderation by including interactions between treatment group and sex-, race-, and age-based groupings. We will test whether sex as a biologic variable modifies the intervention effect, but will be underpowered to detect differences because children are infrequently with a male caregiver when seeking emergency care (10-15% in our pilot data). **Mediation:** We will use Imai's counterfactual mediation method, a very general framework that takes models for the outcome and mediator as inputs, to estimate mediation effects. Traditional mediation analysis can be susceptible to bias due to model misspecification and design limitations and limitations in the classes of statistical models, that can be accommodated (typically linear regressions for both the mediator and outcome) but the Imai framework can accommodate a wide variety of distributions for both the mediator and the outcome; our initial specification will be a logistic model for the binary variables and a linear (Gaussian) model for the numeric variables. We will use a quasi-Bayesian approach to draw from conditional distribution of the mediator given the "treatment" and other covariates, and that of the outcome given the exposure, mediator, and other covariates, to construct hypothesis tests for the proportion mediated; this approach is robustly implemented in the R package mediation.

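### The mediation models do not commit to adjusting for the baseline autonomy and competence scores that the trial already collects

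*Combined protocol and SAP*

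**What the plan says.** The secondary objective in 2.2 is to determine "mediators (Self-Determination Theory constructs of autonomy, relatedness, competence; emotional state at ED recruitment) of the intervention effects at 12-month follow-up". Section 6.2 (SubAim, Mediation) names a counterfactual mediation method with two working models. One is for the mediator given treatment and covariates. The other is "that of the outcome given the exposure, mediator, and other covariates, to construct hypothesis tests for the proportion mediated". The covariates are not listed in either place.

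Elsewhere, 6.2 gives three pieces of guidance on covariates:

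- After the check of balance between randomised groups: "If significant differences are observed, we will adjust for these variables or conduct stratified analyses".
- Under Aim 1, confounders can be added to the GLM(M) where needed.
- Also under Aim 1, the baseline measurement is adjusted for when a single follow-up is analysed. That refers to the outcome.

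Table 1 in 3.3 gives the timing of the candidate mediators. The Treatment Self-Regulation Questionnaire (TSRQ) and the confidence rulers with the Perceived Competence Scale are both scheduled at "ED/Baseline, 6, and 12". The Health Care Climate Questionnaire is taken at 12 months only. The State-Trait Anxiety Inventory is taken at ED/baseline only. Sections 3 and 3.2 place randomisation after the baseline survey.

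**The concern.** Treatment is randomised; autonomy and competence at follow-up are not. A caregiver who is motivated and confident on entry will tend to score high on the follow-up mediator and may also restrain the child better, whatever TCBD does. This baseline level is then a common cause of mediator and outcome. It exists even when the arms are perfectly balanced, so a balance test says nothing about it, and adjusting for the baseline outcome removes only the part that the two baselines share.

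Section 6.2 prefers the counterfactual method partly because it handles many distributions for mediator and outcome. That flexibility does not remove confounding between them. Measured common causes have to be in both models, and the most obvious one is already collected for two of the constructs.

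At stake is the theory claim of the SubAim. The trial could report that TCBD works through autonomy or competence when changes in these do nothing for restraint use.

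**Working it through.** **Plan figures.** The documents state no power or error rate for the mediation test beyond the general rule: "All statistical hypothesis tests and power calculations will use a two-sided = 0.05". There is no mediation figure to reproduce, so the benchmark is a 5% false-positive rate.

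**Inputs from the documents.**
- Analysed sample: "n=204 controls and n=516 TCBD in the initial dichotomy) will be available for analysis at follow-up", that is 204 + 516 = 720 = 0.80 × 900.
- Section 3.2 instead sets out to "assign eligible caregivers to the TCBD intervention or control group in a 3:1 ratio", which makes 720 into 180:540. Since 516/204 = 2.53, the two differ; both splits were used below.

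**Assumed inputs (the documents give none).**
- *a*: shift in the mediator caused by TCBD, 0 to 0.3 SD.
- *r*: correlation of baseline with follow-up mediator, 0.5 to 0.7.
- *g*: direct effect of the baseline mediator on CPaSS, 0.05 to 0.20 SD.
- ρ = 0.3: correlation of baseline mediator with baseline CPaSS.
- Baseline CPaSS coefficient 0.5; total TCBD effect on CPaSS 0.25 SD; true mediator effect zero.

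**Step 1: the bias.** With standardised variables and treatment and baseline CPaSS in the model, leaving out the baseline mediator gives the follow-up mediator a false coefficient

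b\* = r·g·(1 − ρ²) / (1 − r²ρ²).

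The false indirect effect is a·b\*, and the false share mediated is a·b\*/0.25. At a = 0.3:

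| r | g | b\* | a·b\* | share |
|---|---|---|---|---|
| 0.5 | 0.05 | 0.02275/0.9775 = 0.0233 | 0.0070 | 2.8% |
| 0.5 | 0.10 | 0.0455/0.9775 = 0.0465 | 0.0140 | 5.6% |
| 0.6 | 0.15 | 0.0819/0.9676 = 0.0846 | 0.0254 | 10.2% |
| 0.7 | 0.20 | 0.1274/0.9559 = 0.1333 | 0.0400 | 16.0% |

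Simulation gave median reported shares of 5–15% for the last three rows, which agrees. If a = 0 or g = 0, the false indirect effect is zero. The total effect and the TCBD-to-mediator effect contain no bias term, because the baseline mediator is independent of arm.

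**Step 2: the false-positive rate.** Simulated trials at 180:540 used linear models and quasi-Bayesian draws, with baseline CPaSS in both models. Mediation was declared when the 95% interval for the proportion mediated excluded zero.

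| TCBD shift in mediator | Baseline mediator omitted |
|---|---|
| 0 | at most about 5% |
| 0.1 SD | about 0.4–20% |
| 0.2 SD | about 4–62% |
| 0.3 SD | about 8–88% |

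Ranges run over the *r* and *g* above. At 0.3 SD the cells are about 8–11% for (r, g) = (0.5, 0.05), 24% for (0.5, 0.10), 59% for (0.6, 0.15) and 83–88% for (0.7, 0.20). With *g* = 0 at the same shift the rate is about 4%. With the baseline mediator in both models, every case is about 6% or less.

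**Step 3: a second model at 204:516.** With a = 0.3, r = 0.5, a baseline correlation parameter of 0.5 and baseline outcome adjusted, the same test gave 27.2% at g = 0.2 and 51.6% at g = 0.3. With the baseline mediator added these fell to 2.9% and 3.8%. For a binary outcome (runs with no baseline outcome), a = 0.3 gave 9.2% and 30.2% at log odds ratios of 0.2 and 0.4 per SD, against 3.5% and 2.0% with the baseline mediator.

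**The case against.** A reader might infer that the plan refuses baseline adjustment, or that false mediation far above 5% is built into it. The documents support neither. Both models in 6.2 condition on an open set of covariates, so the baseline mediator is unnamed and not excluded. An analyst following the plan could include it. The fault is that nothing requires it.

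A reader might also take the balance rule in 6.2 as the selector of mediation covariates and conclude that a baseline mediator would enter in only about 5% of trials. The plan attaches that rule to the evaluation of randomisation and does not say that it governs the mediation models. All that stands is that the rule does not fill the gap.

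A third tempting reading is that prior motivation is credited to TCBD. It is not. Randomisation keeps the total effect and the TCBD-to-mediator effect unbiased; only the split of the total effect is wrong.

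The size is also open to challenge. Inflation needs both a shift in the mediator and a direct effect of baseline motivation, and the upper ends of the ranges combine the largest assumed correlation with the largest assumed direct effect. Error rates with neither baseline in the model would be higher, but 6.2 adjusts for the baseline outcome in single-follow-up analyses, so they are not a fair picture of the plan.

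Finally, the rate after the fix is near nominal because, in the simulations, the baseline mediator and baseline CPaSS are the only confounders. Other common causes would remain in practice. These objections narrow the point but do not remove it.

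**Conclusion.** The point holds as under-specification with a possible and sometimes large consequence. Section 6.2 does not commit to the baseline mediator, and none of its covariate guidance supplies it. If it is left out, false mediation ranges from no inflation (TCBD does not move the mediator, or baseline motivation has no direct effect) to about 8–88% at a 0.3 SD shift, under assumed correlations and effects that the documents do not give. That TCBD moves the mediator is the sponsor's own hypothesis in the SubAim; the direct effect of baseline motivation is an assumption. The simulations ignore the Month 6 re-randomisation.

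The reach is the secondary SubAim only; Aim 1 and Aim 2 inference is unaffected. The adjustment also does not cover every listed mediator. The Health Care Climate Questionnaire has no baseline value. Emotional state is measured only before randomisation, so it cannot be a mediator of TCBD, and baseline adjustment is not its remedy. This is a free improvement.

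**What to change.** Add to the SubAim in 6.2:

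*For autonomy (TSRQ) and competence (confidence rulers/Perceived Competence Scale), the baseline value of the mediator, the baseline value of the outcome and the randomisation strata are included in both the mediator model and the outcome model, regardless of any test of balance between arms.*

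State in the same place that this adjustment does not apply to the Health Care Climate Questionnaire, which has no baseline value, or to emotional state, which precedes randomisation and should not be listed as a mediator.

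The cost is this wording. The scores are already scheduled in Table 1, and no participants, visits or measures are added.
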